2.1 Primary Objectives

- To characterize the safety and tolerability of loncastuximab tesirine in combination with durvalumab, and to identify the recommended dose and schedule for future studies.

2.2 Secondary Objectives

- To evaluate the antitumor effect of the combination of loncastuximab tesirine with durvalumab.
- To characterize the pharmacokinetic (PK) profile of loncastuximab tesirine when given in combination with durvalumab.
- To evaluate the immunogenicity of loncastuximab tesirine when given in combination with durvalumab.

[REDACTED]

■ [REDACTED]

[REDACTED]

■ [REDACTED]

[REDACTED]

■ [REDACTED]

3 Study Design

Refer to the corresponding section in the protocol.

3.1 Sample Size Consideration

Refer to the corresponding section in the protocol.

3.2 Randomization

This study is not randomized.

3.3 Modifications to the statistical section of the protocol

The trial was terminated early. Therefore, only dose escalation (Part 1) data for enrolled patients will be analyzed and a selected or modified analysis from the statistical section of the protocol will be performed.

4 Statistical methods

All analyses use [REDACTED] or higher. Summary tables will be organized by each dose level; if some dose levels have few patients, then dose levels could be combined into dose ranges. All available data will be used in the analyses, and important data will be included in data listings, sorted by dose level, patient, and by visit within patient. Missing data will not be imputed, except via censoring in survival analyses and as otherwise specified.

Unless otherwise noted, categorical data will be presented using counts and percentages, with the number of patients in the analysis set by treatment group as the denominator for percentages. Percentages will be rounded to one decimal place, except 100% will be displayed without any decimal places and percentages will not be displayed for zero counts. Continuous data, unless otherwise noted, will be summarized using the number of observations (n), mean, standard deviation (std), median, minimum, and maximum. Minima and maxima will be rounded to the precision of the original value, and means, medians, and 95% confidence intervals (CIs) if presented will be rounded to 1 decimal place greater than the precision of the original value. The std will be rounded to 2 decimal places greater than the precision of the original value, up to a maximum of 3 decimal places.

No hypothesis testing will be performed in this study.

4.1 Analysis Sets

4.1.1 Safety Analysis Set

The safety analysis set consists of all patients who receive any study drug.

4.1.2 DLT-evaluable Analysis Set (Part 1)

The DLT-evaluable analysis set consists of all patients in Part 1 who received study drugs and excludes patients who discontinue from the study during the DLT evaluation period without experiencing a DLT. The patients with completed DLT information will be included even if they discontinue early before the end of DLT evaluation period. The DLT evaluation period will be the 21 days after the first durvalumab dose.

4.1.3 Efficacy Analysis Set

The efficacy analysis set consists of patients who receive at least one dose of study drug with a valid baseline and at least one valid post-baseline disease assessment or patients who have documented progression of disease or death at any time after the first dose of study.

4.2 Patient Disposition

For the enrolled patients, the number and percentage of enrolled and treated patients who were on treatment as well as reason for screen failure will be tabulated. For the safety analysis set, the number and percentage of patients who discontinued from study treatment and who discontinued the study for each reason will be tabulated for each dose level.

Patient disposition data will be listed.

4.3 Protocol Deviations

The number and percentage of patients with any important clinical study report (CSR) reportable protocol deviation will be summarized overall and by type of deviation. The pre-defined important CSR reportable protocol deviations are listed below; in addition, any other protocol deviations deemed by ADCT medical to be important CSR reportable deviations will be included in the summary.

1. Patient entered the study even though they did not satisfy the entry criteria
2. Patient received a prohibited concomitant treatment during the study
3. Patient who received the wrong treatment or incorrect dose. For example,
 - Actual dose of study drug was more than 15% off the protocol defined planned dose level.
 - Lonca dosing interval is less than 18 days.

Important protocol deviations will be listed.

4.4 Demographic and Baseline Characteristics

Demographic and baseline characteristics will be tabulated for the safety analysis set by dose level. Variables include the following:

- Sex (female, male)
- Race (white, black or African American, Asian, American Indian or Alaska native, native Hawaiian or other Pacific Islander, other)
- Ethnicity (Hispanic or Latino, not Hispanic or Latino)
- Age (years)
- Age group (< 65, ≥ 65 - < 75, ≥ 75 years)
- Height (cm)
- Weight (kg)
- Body mass index (kg/m²)
- Eastern Cooperative Oncology Group (ECOG) performance status
- Country (Spain, USA)

Demographic and baseline characteristics data will be listed.

4.5 Cancer History and Medications History

Cancer history will be presented for the safety analysis set by dose level. Cancer history will include the following variables:

- Duration since diagnosis
- Non-Hodgkin lymphoma (NHL) subtype (diffuse large B-cell lymphoma, mantle cell lymphoma, follicular lymphoma)
- Disease staging (Stage I, II, III, IV; Subtype E, X, S; Extra-nodal involvement at study entry and number of sites of involvement)
- Cytogenetic analysis (cytogenetic abnormalities: t (2;3), t (2;18), t (3;14), t (3;22), t (8;14), t (8;22), t (11q), t (11;14), del (11q), +12, del (13q), t (14;18), del (17p), t (18;22), BCL2 rearrangement, BCL6 rearrangement, MYC rearrangement, other)

- Immunophenotypic analysis (IgVH status: mutated, unmutated, not applicable; Results of negative, positive or not done for expression BCL2, BCL6, CD3, CD5, CD10, CD19, CD20, CD21, CD23, CD43, CD45, CYCLIN D1, IRF4/MUM1, Ki-67, MYC, and ZAP70)

Prior anticancer procedure or therapy will include the following variables:

- Number of lines of therapy/ regimens per patient
- Any prior surgeries for the current malignancy (yes, no)
- Any prior radiotherapy for the current malignancy (yes, no)
- Reason for stopping prior systemic treatment (progression, toxicity, Completed Treatment, other)
- Best response while on regimen for prior systemic treatment (complete response [CR], partial response [PR], stable disease [SD], progressive disease [PD], not evaluable [NE])
- Any prior stem cell transplant (yes, no)
- Type of transplant (allogenic, autologous, both, other)
- Conditioning therapy (yes, no)

Bone marrow evaluation (bone marrow aspirate and/or bone marrow biopsy) at screening may be listed if applicable. Medical and cancer history data will be listed. Results of cytogenetic analysis and immunophenotypic analysis will be listed. CD19 expression level data will be listed if available. Tumor tissue biopsy collection will not be listed, but will be contained in datasets.

Prior anticancer surgery, radiotherapy, systemic treatment, and stem cell transplant data will be listed.

4.6 Prior or Concomitant Medications (other than anticancer therapies)

All medications taken from ICF signature date or from 14 days before dosing and continuing until 30 days after last dose of study drug are to be reported in the CRF pages.

All medications will be coded using the World Health Organization-Drug Dictionary (WHO-DD) and presented by dose level for the safety analysis set.

- Prior medications are those the patient used prior to first investigational product (IP) intake. Prior medications can be discontinued before first dosing or can be ongoing during the treatment phase.
- Concomitant medications are any treatments received by the patient concomitantly to any IP(s), from first dose (or start of the observation period) to the last dose + 30 days. A given medication can be classified both as a prior medication and as a concomitant medication. Concomitant medications do not include medications started 30 days after the last dose.

Any technical details related to computation, dates, and imputation for missing dates are described in Section 6.

Prior medications will be listed together with concomitant medications. Premedication for dosing will be listed separately.

4.7 Exposure to Treatment

4.7.1 Extent of ADCT-402 Exposure

ADCT-402 exposure will be summarized for the safety analysis set by dose level. The following items will be tabulated.

- Duration of treatment (in days) = last dose date – first dose date +1
- Total number of cycles dose administered
- Total dose administered (in μg and $\mu\text{g}/\text{kg}$)
- Average dose per cycle (in μg and $\mu\text{g}/\text{kg}$)

When actual weight adjusted dose is needed, the last available weight before each infusion will be used. Patients with a BMI $\geq 35 \text{ kg}/\text{m}^2$ will have their dose calculated based on an adjusted body weight as follows:

$$\text{Adjusted body weight in kg} = 35 \text{ kg}/\text{m}^2 * (\text{height in meters})^2.$$

Dose administered at each infusion (μg) is calculated by concentrated IP volume (in mL)* 5 mg/mL *1000 or serially diluted IP volume (in mL)/50* 5 mg/mL *1000; for partial infusion, multiply by (1- volume of dosing solution not administered [in mL]/ 50 mL).

4.7.2 Extent of Durvalumab Exposure

Durvalumab exposure will be summarized for the safety analysis set by dose level. The following items will be tabulated.

- Duration of treatment (in days) = last dose date – first dose date +1
- Total number of cycles dose administered
- Total dose administered (in mg)
- Average dose per cycle (in mg)

For partial infusion, dose administered at each infusion (mg) is calculated as 1500 mg*(1- volume of dosing solution not administered [in mL]/ total volume of dosing solution prepared [in mL]).

Dose delays and dose reductions could also be analyzed if relevant. A cycle is delayed if it starts more than 3 days post-scheduled date. Durvalumab will be given at full dose when resumed after being held for toxicity, i.e., there will be no dose reduction.

Exposure data and infusion details will be listed together.

4.7.3 Prophylactic Medications for Hypersensitivity

Prophylactic medications for hypersensitivity will be listed only.

4.7.4 Subsequent Anticancer Therapy or Procedure

Patients' subsequent anticancer therapies or procedures including systemic therapy, radiation, transplant, or other, along with the start date of new anticancer therapy or procedure will be listed only.

4.8 Safety Analyses

The summary of safety results will be presented by treatment group.

General common rules

All safety analyses will be performed on the safety analysis set, unless otherwise specified, using the following common rules:

- The baseline value is defined as the last non-missing value or measurement taken up to the first dose in the study.
- The analyses of the safety variables will be essentially descriptive and no systematic testing is planned.
- The toxicity grade according to the Common Terminology Criteria for Adverse Events (CTCAE) version 4.0 will be taken into account in the summary. For patients with multiple occurrences of the same event, the maximum grade is used. If a patient has both missing and non-missing severity grades for treatment-emergent adverse events (TEAEs) within the same preferred term (PT), the patient will be counted under the non-missing severity grade.

4.8.1 Dose-limiting Toxicities (Part 1)

DLT data will be listed for Part 1 of the study.

4.8.2 Adverse Events, Serious Adverse Events, and Deaths

4.8.2.1 Analyses of adverse events

The primary focus of adverse event reporting will be on TEAEs. An adverse event (AE) will be considered to be a TEAE if it begins or worsens on or after first dose date and until 30 days after the last dose date, or start of a new anticancer therapy/procedure, whichever comes earlier.

An AE occurring before the first dose or more than 30 days after last dose date or after the start of a new anticancer therapy/procedure will not be included in TEAE displays, but will be listed as non-TEAEs.

If an AE date/time of onset (occurrence, worsening, or becoming serious) is incomplete, an imputation algorithm will be used to classify the AE as pre-treatment, TEAE, or post-treatment. The algorithm for imputing date/time of onset will be conservative and will classify an AE as a treatment-emergent unless there is definitive information to determine it is a non-TEAE (pre- or post-treatment).

Details on classification of AEs with missing or partial onset dates are provided in Section 6.

Analysis of all TEAE(s):

The following TEAE summaries will be generated for the safety analysis set in each dose level.

- Overview of TEAEs, summarizing number of TEAE and number (%) of patients with any
 - TEAE
 - Related TEAE (including possibly related, probably related, or related)
 - Any TEAE \geq Grade 3
 - Serious TEAE
 - TEAE leading to death
 - TEAE leading to permanent treatment discontinuation
 - TEAE leading to ADCT-402 delay or reduction or interruption
 - TEAE with at least one infusion related reaction

For related TEAE and TEAE leading to dose modification (treatment discontinuation, dose delay/reduction/interruption), summary will be broken up for each study drug respectively.

- All TEAEs by PT and all TEAEs with CTCAE Grade \geq 3 by PT, showing number (%) of patients with at least one TEAE, sorted by decreasing incidence of PTs
- All TEAEs by primary System Organ Class (SOC) and PT, showing number (%) of patients with at least one TEAE, sorted by SOC in alphabetic order and decreasing incidence of PTs within SOC. This sorting order will be applied to all other tables, unless otherwise specified.
- All TEAEs by primary SOC, PT and Maximal CTCAE grade, showing number (%) of patients with at least one TEAE, sorted by SOC and PT in alphabetic order. This sorting order will be applied to all other tables, unless otherwise specified.
- All TEAEs with CTCAE Grade \geq 3 by primary SOC, PT and Maximal CTCAE grade
- All related TEAEs by primary SOC, PT and Maximal CTCAE grade (including possibly related, probably related, or related)
- All Serious TEAEs by primary SOC, PT and Maximal CTCAE grade

All TEAEs, all serious adverse events (SAEs), all TEAEs leading to treatment discontinuation, all TEAEs leading to dose reduction, all TEAEs leading to dose delay, all TEAEs leading to infusion interruption, all TEAEs considered infusion related reactions, all TEAEs with fatal outcome and non-TEAEs will be listed.

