- To evaluate the antitumor effect of the combination of loncastuximab tesirine with durvalumab
- To characterize the pharmacokinetic (PK) profile of loncastuximab tesirine when given in combination with durvalumab
- To evaluate the immunogenicity of loncastuximab tesirine when given in combination with durvalumab

[REDACTED]

Endpoints:

Primary Endpoints

- Frequency and severity of adverse events (AEs) and serious adverse events (SAEs)
- Incidence of dose limiting toxicities (DLTs) during the 21 days after the first durvalumab dose (dose escalation only)
- Frequency of dose interruptions and dose reductions
- Changes from baseline of safety laboratory values, vital signs, Eastern Cooperative Oncology Group (ECOG) performance status, and 12-lead electrocardiograms (ECGs)

Secondary Endpoints

- Overall response rate (ORR) according to the 2014 Lugano classification as determined by the Investigator. ORR is the proportion of patients with a best overall response (BOR) of complete response (CR) or partial response (PR)
- Duration of response (DOR) defined as the time from the documentation of first tumor response to disease progression or death
- CR rate defined as the percentage of patients with a BOR of CR
- Relapse-free survival (RFS) defined as the time from the documentation of CR to disease progression or death
- Progression-free survival (PFS) defined as the time between start of treatment and the first documentation of recurrence, progression, or death
- Overall survival (OS) defined as the time between the start of treatment and death from any cause
- Concentrations and PK parameters of loncastuximab tesirine (total antibody, PBD-conjugated antibody, and unconjugated cytotoxin SG3199)
- Anti-drug antibody (ADA) titers and, if applicable, neutralizing activity to loncastuximab tesirine

[REDACTED]

[REDACTED]

[REDACTED]

[REDACTED]

[REDACTED]

Study Design:

This is a Phase 1b, open-label, single-arm combination study with a dose escalation phase (Part 1) followed by a dose expansion phase (Part 2). The study will enroll approximately 75 patients.

A standard 3+3 dose escalation design will be used. The DLT period will be the 21 days after the first durvalumab dose.

The dose expansion phase (Part 2) will consist of 3 cohorts of approximately 20 patients each, one for DLBCL, one for MCL, and one for FL, to obtain additional safety and preliminary antitumor activity information at the maximum tolerated dose (MTD)/RDE.

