1.2.2 Safety and Efficacy of Loncastuximab Tesirine

ADCT-402-101 (NCT02669017) is a first-in-human Phase 1 dose escalation study of loncastuximab tesirine in relapsed or refractory B-cell NHL patients, who have failed or are intolerant to established therapies, or have no other treatment options available. The study design involves a dose escalation phase (Part 1) followed by a dose expansion phase (Part 2). The primary objectives for Part 1 were to evaluate the safety and tolerability of loncastuximab tesirine and to determine the maximum tolerated dose (MTD) and/or the recommended dose(s) to use in Part 2. The primary objective for Part 2 was to evaluate the safety and tolerability of the dose(s) determined in Part 1. The secondary objectives include evaluating the clinical activity of loncastuximab tesirine as measured by ORR, DOR, progression--free survival (PFS), and overall survival (OS).

As of data cut-off date of 03 December 2017, a total of 144 patients with relapsed or refractory B-cell NHL received at least one infusion of loncastuximab tesirine. The median age was 63.5 years (range: 23-86). The median number of previous chemotherapy regimens was 3 (range: 1-10) with 24.3% of patients having prior stem cell transplant.

Treatment-emergent adverse events (TEAEs) were reported in 137 (95.1%) out of 144 patients treated with loncastuximab tesirine. The most common TEAEs (observed in at least in 15% of patients), regardless of relationship to study treatment, were fatigue (42.4%); nausea (27.1%); gamma-glutamyltransferase (GGT) increased (26.4%); anemia (25.7%); edema peripheral (25.0%); dyspnea (18.8%); neutrophil count decreased, platelet count decreased, and thrombocytopenia (18.1% each); rash (17.4%); abdominal pain (16.0%); neutropenia (16.0%); and constipation (15.3%). Grade ≥ 3 TEAEs were reported in 92 (63.9%) patients. The most common Grade ≥ 3 TEAEs (observed in at least in 5% of patients) were neutrophil count decreased (16.0%); GGT increased (14.6%); anemia (12.5%); platelet count decreased (11.8%); neutropenia (11.1); and thrombocytopenia (8.3%).

The following events were considered non-serious adverse drug reactions (ADRs): GGT increased, edema (includes peripheral and facial), neutrophil count decreased, platelet count decreased, thrombocytopenia, neutropenia, and skin-related events (such as rash, maculopapular rash, and erythema).

TEAEs in 16 (11.1%) patients led to treatment discontinuation.

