6.7.2 Treatment of Edema and Pleural Effusion

Peripheral edema and serosal effusions (pleural and pericardial effusions, ascites) have been seen in patients receiving loncastuximab tesirine. Patients should be advised to monitor their weight on a daily basis (preferably each morning around the same time) and notify the study site of weight gain greater than 1 kg from baseline.

Patients with weight gain greater than 1 kg from baseline, new or worsening edema, and/or new or worsening pleural effusion, pericardial effusion, or ascites, should be treated with spironolactone at standard doses. The dose of spironolactone may be titrated as clinically indicated. Additional diuretic support may be added if there is further increase in weight, edema, or effusion.

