9.8.1 Adverse Events

The focus of AE summarization will be on TEAEs. A TEAE is defined as an AE that occurs or worsens in the period extending from the first dose of study drug to 30 days after the last dose of study drug or initiation of new anti-cancer therapy (whichever occurs earlier).

TEAEs will be summarized. Summary tables will be presented to show the number of patients reporting TEAEs by severity grade and corresponding percentages. A patient who reports multiple TEAEs within the same Preferred Term (or System Organ Class [SOC]) is counted only once for that Preferred Term (or SOC) using the worst severity grade.

Separate summaries will be prepared for TEAEs classified as severe or life-threatening (Grade 3 or higher); study drug-related AEs; AEs leading to treatment interruption, modification, or discontinuation; serious AEs; and death.

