9.10 Immunogenicity Analyses

A tiered immunogenicity strategy (Figure 2) will be undertaken to evaluate ADAs by screening and confirmatory assays with titer evaluation, followed by characterization and evaluation of neutralizing capacity as needed. ADA sample collection, banking, and testing in validated and to be validated assays will be according to the new FDA Draft Guidance for Industry (April 2016): ‘Assay Development and Validation for Immunogenicity testing of Therapeutic Protein Products’.

Figure 2 Anti-drug Antibody Tiered Immunogenicity Testing Strategy

Abbreviations: ADA, anti-drug antibody; ADC, antibody-drug conjugate; BSA, bovine serum albumin; mAb, monoclonal antibody; PK, pharmacokinetics.

Results from ADA testing will include tabular summarization for number/proportion of patients with positive pre-dose ADA response, number of patients with post-dose ADA response only, and number of patients with positive ADA response at any time. The denominator will be the total number of patients tested for ADAs in the study.

[REDACTED]

[REDACTED]

10 Data Management and Quality Assurance

The Investigator will maintain accurate source documentation including patient medical records, laboratory reports, ECG strips, and patient diaries.

Investigative site qualified personnel will enter patient data into an EDC system. The analysis data sets will be a combination of these data and data from other sources.

Clinical data management will be performed in accordance with applicable standards and data cleaning procedures to ensure the integrity of the data (e.g., removing errors and inconsistencies in the data). AEs will be coded using the Medical Dictionary for Regulatory Activities (MedDRA). Concomitant medications will be coded using the World Health Organization (WHO) Drug Dictionary.

After database lock, each study site will receive information about all of their site-specific eCRF data as entered into the EDC system for the study, including full discrepancy and audit history. Additionally, a copy of study data from all sites will be created and sent to the Sponsor for storage. The CRO will maintain a duplicate copy for its records. In all cases, patient initials will not be collected or transmitted to the Sponsor.

For detailed instruction on data entry procedures and timelines, please refer to the eCRF Completion Guidelines.

11 Ethical, Regulatory, and Study Management Considerations

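### The by-term adverse event tables have no grouped terms, so neutropenia and thrombocytopenia, each reported under two preferred terms in the single-agent study, may be understated in their individual rows

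*SAP*

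**What the plan says.** The first primary endpoint in the protocol synopsis is "Frequency and severity of adverse events (AEs) and serious adverse events (SAEs". SAP Section 4.8.2.1 starts with an overview table of patients with any treatment-emergent adverse event (TEAE) and with related, Grade 3 or higher, serious, fatal, treatment-discontinuing, dose-modifying and infusion-reaction TEAEs. Every summary table after that is by PT or by system organ class (SOC) and PT, for example "All TEAEs by primary System Organ Class (SOC) and PT, showing number (%) of patients with at least one TEAE". The related and serious tables use the same rows, split by maximum CTCAE grade.

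Protocol Section 9.8.1 removes duplicate counts only within one term or class: a patient with several such events "is counted only once for that Preferred Term (or SOC) using the worst severity grade". Protocol Section 10 states the coding rule: "AEs will be coded using the Medical Dictionary for Regulatory Activities (MedDRA"). Neither document defines a grouped term or a list of synonyms to combine.

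Protocol Section 1.2.2 reports the single-agent study term by term, including "neutrophil count decreased, platelet count decreased, and thrombocytopenia (18.1% each"), with neutropenia on its own line at 16.0%. Its list of adverse drug reactions, however, puts peripheral and facial edema together and puts rash, maculopapular rash and erythema together as skin-related events.

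**The concern.** A PT row answers how many patients had an event coded to that term. The clinical question is how many patients had neutropenia, or thrombocytopenia, under whatever name the site wrote down. When a toxicity is reported under two terms, those rows do not answer it: some patients may appear in both rows and others in only one, and the table does not say which. SOC rows do not help, because they also count unrelated events. Whether the two synonyms even share an SOC depends on the dictionary structure, which the documents do not give.

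The gap is widest in the related and serious tables. Laboratory tables can show how low the counts fell, but not whether the investigator thought the event drug-related or whether it was serious. For edema and skin events no graded laboratory value exists, and under SAP Section 4.8.7 body weight is only listed and significant examination findings are recorded as medical history or AEs. The AE tables are therefore the only planned tabulation of those two toxicities, which the protocol itself describes as groups.

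**Working it through.** **Inputs (Protocol Section 1.2.2, N = 144).** Any grade: neutrophil count decreased 18.1%, neutropenia 16.0%, platelet count decreased 18.1%, thrombocytopenia 18.1%. Grade 3 or higher: 16.0%, 11.1%, 11.8% and 8.3% in the same order.

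**Step 1: reproduce the stated figures.** One patient is 100/144 = 0.69 points, so each one-decimal percentage fits exactly one whole count. Any grade: 26/144 = 18.1%, 23/144 = 16.0%, 26/144 = 18.1%, 26/144 = 18.1%. Grade 3 or higher: 23/144 = 16.0%, 16/144 = 11.1%, 17/144 = 11.8%, 12/144 = 8.3%. The totals given with counts also agree: 137/144 = 95.1% with any TEAE and 92/144 = 63.9% with Grade 3 or higher.

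**Step 2: bound the number of patients with either term.** With counts *a* and *b*, the number with at least one of the two terms lies between max(*a*, *b*), if the smaller group is wholly contained in the larger, and *a* + *b*, if no patient has both. As an illustration only, independence would give *a* + *b* − *ab*/144.

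| Toxicity | a, b | Either term, n | Either term, % | If independent | Larger row short by |
|---|---|---|---|---|---|
| Neutropenia, any grade | 26, 23 | 26 to 49 | 18.1 to 34.0 | 31.1% | 0 to 16.0 points |
| Thrombocytopenia, any grade | 26, 26 | 26 to 52 | 18.1 to 36.1 | 32.9% | 0 to 18.1 points |
| Neutropenia, Grade ≥3 | 23, 16 | 23 to 39 | 16.0 to 27.1 | 25.3% | 0 to 11.1 points |
| Thrombocytopenia, Grade ≥3 | 17, 12 | 17 to 29 | 11.8 to 20.1 | 19.2% | 0 to 8.3 points |

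The last column is (upper count − larger single count)/144, for example (49 − 26)/144 = 16.0 points. The largest relative shortfall is (52 − 26)/52 = 50%.

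**Step 3: scale to this trial.** Protocol Section 9.1 plans about 15 patients in Part 1. At the single-agent any-grade rates, the larger row for either cytopenia would be expected to show 15 × 26/144 = 2.7 patients. The combined figure would be 2.7 to 15 × 49/144 = 5.1 for neutropenia, and 2.7 to 15 × 52/144 = 5.4 for thrombocytopenia. In a dose level of 6 the expected gap is at most 6 × 26/144 = 1.1 patients. One patient under each of two synonyms would read as 1/6 = 17% twice, where the combined count is 2/6 = 33%.

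**Step 4: what the other outputs supply.**
- The overview counts in SAP Section 4.8.2.1 do not depend on the choice of synonym.
- SAP Section 4.8.3 summarizes gradable laboratory results by CTCAE grade, with a worst post-baseline summary over scheduled and unscheduled visits. Graded neutrophil and platelet falls are therefore tabulated whatever the AE term.
- All TEAEs and all serious events are listed.
- No planned table gives the number of patients with related or serious neutropenia or thrombocytopenia across both terms, or with any combined edema or skin event.

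**The case against.** A reader might infer that the primary endpoint itself is understated. The documents do not support that. The endpoint is the frequency and severity of adverse events, not a neutropenia rate, and each PT row is correct for its own label. Laboratory change is a separate primary endpoint, and its grade tables cover the cytopenias. Dose-limiting cytopenias are defined in Protocol Section 6.4.3 by condition and grade, not by coded term, and are listed. Escalation decisions rest with the steering committee (Protocol Section 6.4.4).

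A reader might also infer that the rates shown will be half the true ones. That is only the no-overlap extreme, taken from another study. Overlap may be complete, and nothing shows how sites in this trial report the events. A hidden dose trend cannot be shown from these figures either, and SAP Section 4 allows sparse dose levels to be combined.

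The setting is modest. SAP Section 3.3 restricts the analysis to Part 1 after early termination, the analysis is descriptive, and with about 15 planned patients a combined count can be made from the listing.

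These points limit the size of the problem but do not remove it. Combining terms by hand from a listing means choosing them after the data are seen, and the laboratory tables give neither relatedness nor seriousness and say nothing about edema or rash.

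**Conclusion.** The point holds as a limitation of the by-term AE tables. For this drug, both cytopenias have been reported under two terms in substantial numbers, and the SAP has no row that combines them. On the single-agent figures, the larger PT row could fall short of the combined any-grade rate by 0 to 16.0 points for neutropenia and 0 to 18.1 points for thrombocytopenia, and at Grade 3 or higher by 0 to 11.1 and 0 to 8.3 points. These ranges assume only that the rounded percentages come from 144 patients. Carrying them to this trial assumes similar rates and reporting habits, and the documents do not give the number of patients actually enrolled in Part 1.

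The edema and skin groups rest on the protocol's own grouping in Section 1.2.2, and no size can be put on splitting there. One could read the dose-hold rule in Protocol Section 6.5.1 as making AST, ALT and GGT one toxicity, but it only gives them a shared grade threshold. They are different analytes, already covered by the laboratory shifts. No split is shown for effusions or for the immune-mediated categories of Appendix 3. The change is worth making because it is cheap; no stated figure is wrong.

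**What to change.** Add one table to SAP Section 4.8.2.1: grouped terms by maximum CTCAE grade and dose level, for all, Grade 3 or higher, related and serious TEAEs, with each patient counted once per group. Use four groups:

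- neutropenia and neutrophil count decreased;
- thrombocytopenia and platelet count decreased;
- edema, peripheral and facial;
- the skin-related events named in Protocol Section 1.2.2.

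Fix the list of PTs in each group before database lock. Keep the PT and SOC tables as they are, and cross-refer the two cytopenia rows to the laboratory worst-grade table so that reported events and measured counts can be read together. Groups for effusions and for the Appendix 3 immune-mediated categories are optional. No liver-enzyme group is needed.

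The cost is one extra table and a short term list. It needs no new data and changes no existing output.
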